### C.9. Outcomes

Primary outcome:

- Guideline-adherent management: Proportion of pre-specified, guideline-consistent critical management actions (diagnostics and treatments) completed per vignette (proportion 0-1). Participant responses recorded at the initial assessment and post-investigation stages will be scored against a gold-standard answer key derived from WHO guidelines (Basic Emergency Care assessment checklists, ETAT performance checklists, Integrated Management of Childhood Illness checklists). Scoring will be performed by two independent assessors, blinded to allocations, mapping free text to binary items (performed correctly vs. not performed/incorrect). Disagreements will be resolved by consensus.

Secondary Outcomes:

- Triage accuracy: Correct assignment to Interagency Integrated Triage Tool (IITT) category (Red/Emergency, Yellow/Urgent, Green/Non-urgent) compared with the case-specific expected category (binary). Scoring will be performed by two independent assessors, blinded to allocations.
- Disposition appropriateness: Appropriateness of the disposition decision (hospitalize, discharge) compared with case-specific expected disposition in the answer key, based on

WHO/Uganda guidelines (binary). Scoring will be performed by two independent assessors, blinded to allocations.

- Diagnostic accuracy: Correctness of working impression (initial stage) and final diagnosis (post-investigation stage), compared with case-specific diagnostic labels in the answer key, based on WHO/Uganda guidelines (binary). Scoring will be performed by two independent assessors, blinded to allocations, mapping free text to binary items (performed correctly vs. not performed/incorrect).
- Guideline-adherent evaluation (process quality): Proportion of critical history and examination items elicited by the participant during the vignette, compared with case-specific list of critical items derived from WHO guidelines (proportion 0-1). Scoring will be performed by two facilitators during each simulation session using the facilitator tick-box logs.
- Time to completion: Duration needed to complete each vignette, measured by facilitators (continuous).
- Usability: Total score on System Usability Scale (SUS), a widely validated 10-item tool for evaluating software systems in healthcare and other fields (continuous).
- Perceived usefulness, trust, satisfaction, and feasibility: assessed via structured Likert-scale items, adapted from the Technology Acceptance Model (TAM) and related implementation frameworks (categorical), and via brief semi-structured interviews.

### C.10. Data Collection and Management

Data will be collected electronically using Kobo Toolbox, an open-source, web-based platform developed by the Harvard Humanitarian Initiative for data collection in resource-limited and field settings (<https://www.kobotoolbox.org/>).

- Baseline data: Prior to randomization, participants will complete a baseline survey capturing demographic and professional characteristics, prior emergency training, and digital literacy (**Appendix B**).
- Simulation data: During each vignette, two facilitators (emergency medicine clinicians from the study team) will deliver cases, log process measures using structured tick-box forms (**Appendix C**), and capture start/end times. Any discrepancies will be reconciled immediately after the session. Participants will record clinical decisions directly into Kobo Toolbox forms at predefined stages (**Appendix D**).
- Outcome scoring: Responses will be exported in de-identified forms and scored by two independent assessors, blinded to allocation, using pre-defined gold-standard answer keys (**Appendix E**). The two assessors will be two clinicians not involved in App or case development. Discrepancies will first be discussed by the two reviewers to reach consensus; if disagreement persists, a third senior adjudicator (not involved in App or case development) will provide the final decision.
- Post-simulation survey and interview: After completing sessions that involve App use, participants will complete a structured electronic questionnaire assessing usability (SUS), perceived usefulness, trust, satisfaction, and feasibility (**Appendix F**). To complement these quantitative measures, the two facilitators will also conduct brief semi-structured interviews with each participant immediately after their simulation session (**Appendix G**). Interviews will not be audio-recorded; instead, facilitators will take contemporaneous field notes, which will be expanded into detailed summaries for subsequent qualitative analysis.

### C.11. Statistical Analysis

All analyses will follow the intention-to-treat principle. For vignette-level outcomes, if a participant does not complete an entire scenario, that scenario will be excluded from analysis. Within completed scenarios, missing or blank responses will be treated as incorrect (i.e., non-adherent), on the assumption that an unanswered item reflects lack of knowledge or failure to act. For survey outcomes, only available responses will be analyzed, with no imputation. Descriptive statistics will therefore be based on the number of participants who provided a response to each item. The number of missing scenarios and survey responses will be reported.

The primary analysis will follow a crossover design, with each participant contributing observations under both study conditions (App-assisted vs. control) across distinct but content-equivalent case scenarios:

- Guideline-adherent management: Analyzed as a bounded proportion (0-1) using a generalized linear mixed-effects model with binomial distribution and logit link. The model will include fixed effects for study arm (App vs. control), period (first vs. second session), sequence (allocation order), scenario type (diarrhea, dyspnea, seizure), cadre (clinical officers vs nurses), years of experience (continuous), baseline comfort in using mobile Apps (dichotomous). Random intercepts will be specified for participant to account for repeated measures. Results will be reported as adjusted mean differences with 95% CIs. Inter-rater reliability will be assessed using Cohen's  $\kappa$  for individual items and intraclass correlation coefficients (ICC) for total checklist scores.
- Triage appropriateness, disposition appropriateness, and diagnostic accuracy: Each will be analyzed as binary outcomes (correct vs. incorrect) using mixed-effects logistic regression, with the same fixed and random effects structure as above. Results will be reported as adjusted odds ratios with 95% CIs. Inter-rater agreement will be evaluated using Cohen's  $\kappa$ .
- Guideline-adherent evaluation (proportion score): Analyzed as a bounded proportion (0-1) using a generalized linear mixed-effects model with binomial distribution and logit link, with the same fixed and random effects as above. Results will be reported as adjusted mean differences with 95% CIs. Inter-rater reliability will be assessed using Cohen's  $\kappa$  for individual items and intraclass correlation coefficients (ICC) for total checklist scores.
- Time to case completion (minutes): Analyzed as a continuous outcome using a linear mixed-effects model. Results will be reported as adjusted mean differences with 95% CIs.

As a sensitivity analysis, a first-exposure parallel analysis will be conducted, in which only the first period for each participant is analyzed. This eliminates potential carryover or learning effects, at the cost of reduced sample size. Findings from the crossover and first-exposure analyses will be compared to assess robustness. Multiplicity across secondary outcomes will be managed by treating the crossover analysis of the primary outcome as the only confirmatory analysis, with all secondary outcomes considered exploratory.

Survey outcomes, including SUS scores and additional Likert-scale items (perceived usefulness, trust, satisfaction, feasibility), will be summarized descriptively and reported as medians with interquartile ranges or proportions, as appropriate.

Qualitative data will be analyzed by two researchers using inductive thematic analysis to identify key themes related to usability and feasibility, and to guide further App refinement.

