## **C.4. Sample Size**

This pilot study will use a feasibility-based sample size, determined by the total number of OPD clinicians available at [name] Hospital. We anticipate enrolling approximately 16 participants, representing all nurses, clinical officers, and nursing assistants currently working in the OPD of [name] Hospital. Each participant will complete 12 simulated scenarios, yielding an estimated 192 scenario-level observations. While not powered to detect small effect sizes, this sample is deemed to be sufficient to assess feasibility, refine study procedures, and provide preliminary effect estimates to inform the design and power calculations of a subsequent larger trial.

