### C.7. Intervention and Control

Experimental arm (OASES App): Participants will use the OASES tablet-based CDSS, which incorporates the Interagency Integrated Triage Tool (IITT) and three condition-specific algorithms (diarrhea, dyspnea, and seizures) derived from WHO and Uganda Clinical Guidelines. No formal training sessions will be conducted; however, participants will receive a brief orientation walk-through of the App immediately prior to its use.

Control arm (standard practice): Participants will manage simulated cases without the App, relying on their usual knowledge and clinical experience. Standard resources available in OPD, including paper-based versions of the IITT and Uganda Clinical Guidelines, will be available for reference.

All participants will complete both arms using a crossover design, with a washout period of at least one week between conditions. During the washout, participants will return to their normal OPD duties without access to the OASES App. No additional clinical teaching or training will be provided during the study period.

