### C.8. Simulation and Scenarios

Each participant will complete 12 facilitated clinical vignette scenarios, with six scenarios per study arm (two diarrhea, two dyspnea, and two seizures). Scenarios will be adapted from WHO training materials for emergency care (e.g., *Basic Emergency Care* course, *Emergency Triage Assessment and Treatment* guidelines) and tailored to reflect common emergency presentations in the OPD of [name] Hospital. Both adult and pediatric cases will be included, varying in severity and presentation to capture the spectrum of conditions typically encountered. Draft cases will undergo expert review and pilot testing with representative clinicians to ensure clarity, realism, and contextual relevance. Cases will be designed in matched pairs to ensure comparable content and difficulty between study periods, with equivalence determined by expert review and pilot testing. Scenarios will be balanced for complexity, number of critical actions, and expected completion time.

Cases will be delivered verbally by a trained facilitator, who will respond only to participant questions to simulate real-world information gathering. Facilitators will log which key history and examination items are elicited using a structured tick-box script.

At two predefined points in each vignette, participants will record their diagnostic and treatment plan:

1. Initial assessment stage – working impression, immediate treatments, and diagnostic tests ordered.
2. Post-investigation stage – final diagnosis, disposition decision, treatment plan and follow-up plan.

Each participant's simulation session will last approximately one hour. All sessions will be scheduled during off-duty hours to ensure voluntary participation and to avoid disruption of patient care.

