### Participant instructions (to be read aloud by the facilitator)

Thank you for joining this simulation session. You will be presented with a patient case, just as if you were in the OPD. Please ask me any questions you think are important for history, examination or investigations—I will only give you the information you request. At two points, I'll pause and ask you to record your impression, tests, treatments, and final decisions on the tablet form. Each case will take about 10 minutes, and you will complete 12 cases in total across two sessions.

When you are using the OASES App, it will guide you step by step through case evaluation and suggest possible treatments and diagnostic tests. However, the App could be wrong or incomplete, so you are free to follow its recommendations or decide differently if you think another approach is better for the patient.

There are no right or wrong answers. Your responses are confidential, and you may withdraw any time. This is not an exam, but part of a research study to evaluate the OASES App.

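### Section C.11 claims intention-to-treat but drops every scenario not completed in full, so stopping a case removes it while leaving answers blank lowers the score

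*Combined protocol and SAP*

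**What the plan says.** Section C.11 opens with "All analyses will follow the intention-to-treat principle". For vignette-level outcomes it then states that "if a participant does not complete an entire scenario, that scenario will be excluded from analysis". The next rule goes the other way: "Within completed scenarios, missing or blank responses will be treated as incorrect (i.e., non-adherent"), on the reasoning that an unanswered item shows missing knowledge or a failure to act.

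The exclusion applies to all vignette-level outcomes: the primary adherence score, triage, disposition, diagnosis, process quality and time. The section does not define a completed scenario. On reporting it promises only that "The number of missing scenarios and survey responses will be reported", without a split by arm, period or reason. Its one sensitivity analysis uses the first period only. It names the crossover analysis of the primary outcome as the sole confirmatory analysis.

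Under section C.8 and Appendix D, answers are recorded at two stages. Stage 1 holds triage category, working impression, immediate treatments and tests. Stage 2 holds final diagnosis, disposition, and treatment and follow-up plan.

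**The concern.** Whether a scenario is completed is known only after randomisation and may depend on the condition in which it was attempted. Excluding on that basis is a completers-only rule, not intention-to-treat.

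The rule also sits badly with the plan's own treatment of blanks. The reasoning given for scoring a blank as incorrect applies at least as well to a clinician who gets stuck and stops, yet that case leaves the analysis.

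If stopped cases are mostly those going badly, and one arm has more of them, that arm's mean is raised by their removal. The bias would enter the only confirmatory analysis. It would also enter the effect estimates that section C.4 wants for planning a larger trial. Times in the arm with more stopped cases could look somewhat shorter for the same reason.

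**Working it through.** **Planned observations.** Section C.4: "We anticipate enrolling approximately 16 participants", each completing 12 scenarios. 16 × 12 = 192, which matches the plan's figure. Section C.8 gives six scenarios per condition, so 16 × 6 = 96 per arm. The plan has no power calculation and no assumed non-completion rate.

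**The two rules side by side.** Take two participants with identical Stage 1 answers. One submits Stage 2 with every field blank. If that counts as completed, the scenario is kept and each Stage 2 item is scored incorrect. The other stops after Stage 1, and the whole scenario is excluded, including a triage answer that was fully observed and the treatments and tests that form part of the primary score. The recorded clinical content is the same and the handling is opposite. Which rule applies turns on a definition that the plan does not give.

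**What would detect or correct this.** The first-period analysis has no different rule for stopped scenarios. An overall count of missing scenarios cannot show imbalance between arms. The facilitator summary in Appendix C has start time, end time and free-text notes, but no field for completion status or reason. The primary model has a random intercept for participant and a fixed effect for scenario type; neither accounts for loss that depends on performance in the particular case.

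**Size of the bias on adherence.** Let p be the App mean over all 96 scenarios with unrecorded actions scored as not performed, m the number excluded, and q the mean score that those m would have had.

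- Mean of the remaining scenarios = (96p − mq) / (96 − m)
- Bias = that mean − p = m(p − q) / (96 − m)

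Assumptions, none of them from the documents: p = 0.60 in both arms (no true effect), no control scenarios excluded, q from 0.2 to 0.4. These are differences in simple means, not output of the planned logistic mixed model.

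| App scenarios excluded | q = 0.4 | q = 0.2 |
|---|---|---|
| 5 of 96 | 5 × 0.2 / 91 = 0.011 | 5 × 0.4 / 91 = 0.022 |
| 10 of 96 | 10 × 0.2 / 86 = 0.023 | 10 × 0.4 / 86 = 0.047 |
| 16 of 96 | 16 × 0.2 / 80 = 0.040 | 16 × 0.4 / 80 = 0.080 |

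With q = 0.6 the bias is 0, because the excluded cases are then like the rest. If the same numbers were lost from control only, the sizes would be equal and the sign reversed. The last row is one scenario per participant (16/96 = 16.7%). If a session limit existed, this is the most that could be started but unfinished, since only one case can be in progress when a session ends.

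**Time to completion.** A simulation assumed a hard session cut-off at 60 to 75 minutes, control cases of 10 minutes, App cases of 12 minutes, an orientation of 5 to 10 minutes inside the session, a between-person SD of 1.5 and a within-person SD of 2 minutes. The true difference of 2.0 minutes was observed as 1.8 to 1.9, a shortfall of about 0.1 to 0.2 minutes. With no cut-off there were no time-driven exclusions and no shortfall.

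**The case against.** A reader might infer that the App session has the tighter time budget, so that App cases will time out, exclusion will favour the App, and its time cost will be hidden. The ingredients are there: "Each participant's simulation session will last approximately one hour" (section C.8), "Each case will take about 10 minutes, and you will complete 12 cases in total across two sessions" (participant instructions, Appendix C), and, for the App only, "participants will receive a brief orientation walk-through of the App immediately prior to its use" (section C.7). Six cases at 10 minutes make 60 minutes, which leaves no slack. If the orientation took an assumed 5, 10 or 15 minutes of that hour, 9.2, 8.3 or 7.5 minutes per case would remain.

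The documents do not support that reading. Both durations are approximate, no session or case limit is stated, and the orientation is not said to fall inside the hour. Section C.9 defines time as the duration needed to complete a vignette, which suggests that cases run until finished. The App guides users step by step, so unaided control participants could be the ones who stop. Even under an assumed cut-off, the time difference shrinks by about 5% to 10%; it does not vanish.

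Two further objections carry weight. This is a feasibility-sized pilot that already undertakes to count missing scenarios. And scoring everything unrecorded as not performed is a worst-case rule, which penalises an arm when a case stops because of a device fault or an interruption. The first lowers the severity. The second calls for a sensitivity analysis. Neither reconciles the exclusion with the stated principle or with the rule for blanks.

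**Conclusion.** The point stands as an internal contradiction with a possible bias, and it should be fixed. That the exclusion rule is not intention-to-treat and conflicts with the handling of blanks follows from the text alone. The bias is conditional: it requires non-completion to differ by arm and to be related to performance. Under the stated assumptions it is about 1–2, 2–5 or 4–8 percentage points for 5, 10 or 16 lost App scenarios, in favour of whichever arm loses more, and nil if no scenario is left incomplete. Time to completion may be modestly understated in the arm with more stopped cases. A tighter App time budget, a predictable advantage to the App and a hidden time cost are not established.

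**What to change.** 1. Define a completed scenario in section C.11. State whether any session or case time limit applies and whether the App orientation counts towards the hour.
2. In the primary analysis, keep every started scenario in its randomised condition. Use the answers recorded and score unrecorded actions as not performed, which extends the plan's own rule for blanks. Treat only never-started scenarios as missing.
3. Treat time in stopped cases as censored at the recorded end time.
4. Add a completion status and a reason for stopping to the facilitator summary in Appendix C. Report stopped and never-started scenarios by arm, period and reason.
5. Keep the completed-only analysis as a sensitivity analysis. Add another that excludes cases stopped for reasons unrelated to performance, such as a device fault or an interruption.

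The cost is SAP wording, two short additions to a form, and analysis time. The form must change before data collection, because reasons for stopping cannot be reliably reconstructed afterwards. The downside is that a few low scores enter the primary analysis, some of them perhaps not the clinician's doing; the last sensitivity analysis shows how much they matter.

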### **Stage 1 – Initial Assessment**

- Triage Category (according to IIT criteria):
  - Red (Emergency)
  - Yellow (Urgent)
  - Green (non-urgent)
- What is your working impression based on this initial evaluation? (free text)
- Which treatments would you start immediately? (free text)
- Which diagnostic tests would you request at this stage? (free text)

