## Appendix E. Scoring Checklist for External Assessor with Gold Standard

### External Assessor Instruction:

Task: evaluate participants' responses in Kobo Toolbox against the gold-standard checklist for each case scenario. Score according to WHO and Uganda Clinical Guidelines.

How to score:

- Flag each item where the participant's response matches or is clinically equivalent to the gold standard.
- Leave blank if the response is absent, incorrect, or inappropriate.
- Do not infer beyond what is explicitly written by the participant.

Domains:

- Diagnostics: Correct if all indicated tests are ordered and unnecessary tests are avoided.
- Treatments: Correct if the participant specifies the correct plan, dose/volume, delivery/reassessment, and avoids harmful or unnecessary therapies.
- Diagnosis, triage, and disposition: Correct if the participant's answer matches the gold-standard label/category for the scenario.

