### Example Case (A001: Pediatric Diarrhea)

Patient: 12 years, 12 kg, MUAC 13 cm, watery diarrhea, vomiting, some dehydration, no danger signs

Gold Standards:

- Triage Category: Yellow (Urgent; some dehydration, no danger signs)
- Immediate Treatments: Only Plan B rehydration: ORS  $\approx 75$  mL/kg ( $\approx 900$  mL) over 4 hours, small frequent sips, reassess at 4 h; continue breastfeeding
- Investigations: None (child alert, afebrile, no severe dehydration, no red flags), malaria test (MRDT or B/S) acceptable in Kalongo due to local epidemiology
- Diagnosis: Diarrhea with some dehydration (acceptable: "acute watery diarrhea," "AWD," "viral gastroenteritis with some dehydration")
- Disposition: Discharge
- Treatment Plan: No antibiotics (no blood in stool, no cholera outbreak); supportive therapy such as paracetamol if febrile acceptable
- Follow-up Plan: since patient has improved after 4 hr observation, discharge with plan A = extra fluids, continue feeding/breastfeeding, return precautions (worsening dehydration, blood in stool, persistent vomiting, convulsions, lethargy, inability to drink); optional zinc supplements (not available in Kalongo)

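### Blank answers are scored as incorrect, yet in the supplied key the correct answer on tests can be none, so a correct but unwritten decision counts as an error in the primary outcome

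*Combined protocol and SAP*

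**What the plan says.** Section C.11 sets the rule for gaps inside a completed vignette: "Within completed scenarios, missing or blank responses will be treated as incorrect (i.e., non-adherent". It gives its reason: "on the assumption that an unanswered item reflects lack of knowledge or failure to act".

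Appendix E gives the assessors three instructions that bear on the same situation:
- "Leave blank if the response is absent, incorrect, or inappropriate"
- "Do not infer beyond what is explicitly written by the participant"
- "Diagnostics: Correct if all indicated tests are ordered and unnecessary tests are avoided"

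The one worked key, case A001 in Appendix E, reads: "Investigations: None (child alert, afebrile, no severe dehydration, no red flags". It also accepts a malaria test.

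The participant form in Appendix D asks: "Which diagnostic tests would you request at this stage? (free text". It shows no option for none and no instruction to write it, and it does not say whether the field must be filled.

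Section C.9 builds the primary outcome from the diagnostic and treatment items, with free text mapped to binary scores. Section C.11 promises counts of missing scenarios and missing survey responses, but not of blanks within scenarios. Its only sensitivity analysis restricts the data to the first period.

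**The concern.** The reason given in C.11 fits an item that calls for an action. It does not fit an item whose correct answer is to do nothing, because an empty field is then a natural way to record the right decision. Under the C.11 rule that decision becomes non-adherence.

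The item belongs to the primary outcome, whose crossover analysis is the only one that C.11 calls confirmatory, and C.4 intends the estimates to feed the power calculation of a larger trial. The planned analyses would not reveal the problem, since neither blanks by item nor a different treatment of them is reported. Nor can it be repaired afterwards: once the form is submitted, a deliberate none and a skipped question look the same.

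**Working it through.** **Step 1. The rules applied to the A001 investigations item.**

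| Participant | C.11 blank rule | Appendix E, absent response | Appendix E, diagnostics definition |
|---|---|---|---|
| Writes none | not triggered | not triggered | correct |
| Writes malaria test only | not triggered | not triggered | correct, since the key accepts it |
| Decides on none, leaves the field empty | incorrect | no credit | correct: nothing indicated is missing, nothing needless is ordered |
| Skips the question | incorrect | no credit | correct on its face |

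The third and fourth rows give identical data. The rules disagree on both, and the C.11 rule marks the third row wrong. A participant who writes the merely acceptable test is credited, while one who makes the gold-standard choice without writing it is not.

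**Step 2. Weight of one false failure.** The assessor sheet in Appendix E has six boxes. Three are diagnostic or treatment items (immediate treatments, investigations, treatment and follow-up plan). One wrongly failed box costs 1/3 of the vignette score if those three count, as C.9 suggests, or 1/6 if all six count.

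**Step 3. Effect on the comparison between arms.** The plan's own count reproduces: 16 participants x 12 scenarios = 192 observations, and 16 x 6 = 96 per arm. The fix does not change it.

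For an item whose key is none, let q be the probability that the participant correctly decides on none, and b the probability that a correct none is left unwritten (C = control, A = App). Then:
- observed proportion correct = q(1 - b)
- bias in App minus control = qC x bC - qA x bA

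The documents give neither q nor b. The values below are assumptions chosen to show the range.

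| qC | qA | bC | bA | True difference | Observed difference | Bias |
|---|---|---|---|---|---|---|
| 0.6 | 0.6 | 0.2 | 0.2 | 0 | 0 | 0 |
| 0.6 | 0.6 | 0.3 | 0.1 | 0 | 0.12 | +0.12 |
| 0.6 | 0.6 | 0.1 | 0.3 | 0 | -0.12 | -0.12 |
| 0.5 | 0.8 | 0.2 | 0.2 | 0.30 | 0.24 | -0.06 |
| 0.5 | 0.8 | 0.5 | 0.5 | 0.30 | 0.15 | -0.15 |
| 0.5 | 0.8 | 0.3 | 0.1 | 0.30 | 0.37 | +0.07 |
| 0.5 | 0.8 | 0.1 | 0.3 | 0.30 | 0.11 | -0.19 |

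For example, the fourth row is 0.8 x 0.8 - 0.5 x 0.8 = 0.64 - 0.40 = 0.24. Blanking is equal in the two arms there, yet false errors are more frequent under the App (0.8 x 0.2 = 0.16) than under control (0.5 x 0.2 = 0.10). Control has more false errors only if bC/bA exceeds qA/qC, which is 0.8/0.5 = 1.6 in that setting.

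**Step 4. On the vignette score.** Bias on the mean score = item bias x share of vignettes with such an item / number of boxes. The extremes of the table, -0.19 and +0.12, give:
- every vignette has one such item, three boxes: -0.19/3 = -0.063 to 0.12/3 = +0.040
- every vignette, six boxes: -0.032 to +0.020
- one vignette in six, three boxes: -0.19/18 = -0.011 to 0.12/18 = +0.007
- one vignette in six, six boxes: -0.005 to +0.003

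If b = 0 in both arms, which is what an explicit none entry aims at, the bias is zero. This is plain arithmetic on proportions and ignores the covariates of the planned model.

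**The case against.** The strongest reply is that the rules do not all point the same way. The diagnostics definition in Appendix E would let an assessor credit the blank, so an error is not inevitable. That is right, and the accurate description is a conflict between rules. But C.11 is the analysis rule and allows no exception, and two assessors following the same page could score the same blank differently.

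Exposure may also be small. The form is free text, so none can be typed; the facilitator asks participants to record their tests; a malaria test is accepted in A001; and the Kobo fields may have been set as required without the protocol saying so. These points limit the likely size. They do not settle the scoring, and C.11 itself provides for blanks.

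Two stronger readings are tempting, and the documents support neither.
- *The artefact favours the App.* A reader might infer this because the participant script in Appendix C says that the App proposes tests and treatments. If 1 to 3 of 6 cases had such an item and control had 20% to 50% more blanks, with three boxes, the spurious benefit would run from 1/6 x 0.2 x 1/3 = 0.011 to 3/6 x 0.5 x 1/3 = 0.083. But the documents give no blank rates and do not say that the App displays none. That calculation admits only excess blanks in control and treats every one as a correct decision.
- *The antibiotic entry is an equal example.* The A001 treatment plan begins "No antibiotics (no blood in stool, no cholera outbreak". However, treatment and follow-up share one field and one assessor box, and the key also expects written follow-up content, so a wholly empty field is incorrect anyway. What remains unclear is only whether a written plan that does not mention antibiotics earns the avoidance element.

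**Conclusion.** The point holds as a scoring rule that is wrong as written. Under C.11, a correct decision to order no test in A001, left unwritten, is counted as non-adherent in the primary outcome, while Appendix E contains one instruction that agrees and one that disagrees. The cost is 1/3 or 1/6 of that vignette's score, depending on which boxes count.

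The sign and size of any bias between arms cannot be determined. Under the assumed values, the shift in the mean vignette score runs from -0.063 to +0.040 if every vignette carries such an item among three boxes, and from about -0.011 to +0.007 if one in six does. With only one key supplied, the true share is unknown. One in six per arm would follow if A001's matched partner also has none as its key and no other case does, which is itself an assumption. Confidence is high on the conflict; on direction the documents are silent.

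**What to change.** Before the first session:
- In Kobo, make the test and treatment fields required in both arms, with an explicit 'None needed' choice beside the free text. The choice may prompt participants slightly, but it does so equally in both arms.
- In Appendix E, score 'None needed' as correct where the key is none. State that elements calling for something to be avoided are met unless the unwanted action is written, and reconcile this with the instructions on absent responses and inference.
- In C.11, limit the rule that a blank is incorrect to items that require an action.
- In C.11, report blanks by item and arm, and add a sensitivity analysis that rescores as correct any remaining blanks on items whose key is none.

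The cost is a form setting and a few sentences in C.11 and Appendix E, with no extra participants or staff. If responses have already been collected, only the scoring clarification, the blank counts and the rescoring analysis remain available. They would bound the problem without removing it.
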